### 7.3.5. Adverse Events and Serious Adverse Events

Detailed information related to the collection and reporting of AEs and SAEs in [Section 8](#).

The Investigator and any qualified designees are responsible for detecting, documenting, and recording events that meet the definition of an AE or SAE and remain responsible for following up AEs that are serious, considered related to study treatment or study procedures, or that caused the patient to discontinue study drug (see Section 6).

#### 7.3.5.1. Pregnancy Testing

Pregnancy testing will be performed only for females of childbearing potential. A negative serum hCG pregnancy test must be obtained at Screening (within 2 days before study treatment administration) and at the end of treatment. Pregnancy testing may be performed if clinically indicated during the study.

#### 7.4. Pharmacokinetic Assessments

Pharmacokinetic (PK) assessment will be performed on a subset of patients. Blood draws for PK analysis of approximately 2.0 mL will be collected for the measurement of plasma concentrations of selinexor at  $4 \pm 1$  hr,  $24 \pm 4$  hr post dose on Day 1 and predose on Days 3 and 5. Instructions for the collection and handling of biological samples are provided in the Laboratory Manual. The actual date and time (24-hour clock time) of each sample and selinexor dose will be recorded.

If a patient experiences emesis within the first hour of selinexor dosing, no PK samples will be collected for that dose.

Plasma PK samples will be shipped to a bioanalytical laboratory for analysis. Details for collection and processing of PK samples can be found in the Laboratory Manual. Plasma samples will be analyzed via a validated high-performance liquid chromatography/tandem mass spectrometry (HPLC/MS-MS) method for plasma selinexor.

#### 7.5. Cytokine Assessments

Blood draws for cytokine analysis of approximately 2.5 mL will be collected according to the Schedule of Assessments Table. We will be testing cytokines and other plasma proteins and compare their levels to assess the efficacy of selinexor in the reduction of cytokines known to be elevated in COVID-19 patients. Exact details on the collection, preparation, storage and delivery of the samples will be included in the Clinical Protocol Lab manual.

#### 7.6. Leukocyte Phenotyping

For Leukocyte Phenotyping, blood will be collected according to the Schedule of Assessments Table. Exact details on the collection, preparation, storage and delivery of the samples will be included in the Clinical Protocol Lab manual.

#### 7.7. Viral Assessments

CCI

## 8. ADVERSE EVENTS

### 8.1. Information on Reporting Adverse Events

#### 8.1.1. Definitions

- *Adverse event (AE)*: Any untoward medical occurrence in a patient or clinical investigation subject administered a pharmaceutical product and which does not necessarily have to have a causal relationship with this treatment. An AE can therefore be any unfavorable and unintended sign (including an abnormal laboratory finding, for example), symptom, or disease temporally associated with the use of study treatment, whether or not considered related to the study treatment.
- *Life-threatening adverse event or life-threatening suspected adverse reaction*: An adverse event or suspected adverse reaction is considered "life-threatening" if, in the view of either the investigator or sponsor, its occurrence places the patient or subject at immediate risk of death. It does not include an adverse event or suspected adverse reaction that, had it occurred in a more severe form, might have caused death.
- *Treatment-emergent adverse event (TEAE)*: Any event that was not present prior to the initiation of study treatment or any event already present that worsens in either intensity or frequency following exposure to study treatment.
- *Serious adverse event (SAE)*: Any untoward medical occurrence that, at any dose, results in death; is life threatening (ie, an event in which the patient was at risk of death at the time of the event; it does not refer to an event that hypothetically might have caused death if it were more severe); requires inpatient hospitalization or prolongation of existing hospitalization; results in persistent or significant disability/incapacity; or is a congenital anomaly/birth defect. Important medical events that may not result in death, be life-threatening, or require hospitalization may be considered serious when, based upon appropriate medical judgment, they may jeopardize the patient or subject and may require medical or surgical intervention to prevent one of the outcomes listed in this definition. Examples of such medical events include allergic bronchospasm requiring intensive treatment in an emergency room or at home, blood dyscrasias or convulsions that do not result in inpatient hospitalization, or the development of drug dependency or drug abuse. (See Section 8.2.1.3 for additional information about SAE reporting.)
- *Suspected adverse reaction*: Any adverse event for which there is a reasonable possibility that the drug caused the adverse event. For the purposes of IND safety reporting, "reasonable possibility" means there is evidence to suggest a causal relationship between the drug and the adverse event. Suspected adverse reaction implies a lesser degree of certainty about causality than adverse reaction, which means any adverse event caused by a drug.
- *Unexpected adverse event or unexpected suspected adverse reaction*: An adverse event or suspected adverse reaction is considered "unexpected" if it is not listed in the investigator brochure or is not listed at the specificity or severity that has been observed; or, if an investigator brochure is not required or available, is not consistent

with the risk information described in the general investigational plan or elsewhere in the current application, as amended. For example, under this definition, hepatic necrosis would be unexpected (by virtue of greater severity) if the investigator brochure referred only to elevated hepatic enzymes or hepatitis. Similarly, cerebral thromboembolism and cerebral vasculitis would be unexpected (by virtue of greater specificity) if the investigator brochure listed only cerebral vascular accidents. "Unexpected," as used in this definition, also refers to adverse events or suspected adverse reactions that are mentioned in the investigator brochure as occurring with a class of drugs or as anticipated from the pharmacological properties of the drug, but are not but are not specifically mentioned as occurring with the particular drug under investigation.

### **8.1.2. Recording of Adverse Events**

All AEs that begin or worsen after the patient has provided informed consent will be recorded. Those AEs that occur prior to study dosing, can be captured in the patient's baseline conditions, however if any of these AEs are considered, serious, these are to be reported both to Pharmacovigilance and documented in the eCRF AE log. For events that are considered by the Investigator to be related to the study drug, the monitoring of the AE should be continued through the end of the study, for at least 30 days following last dose of study drug (if the end of the study is within 30 days of the last dose of study drug), or until the AE has resolved.

Investigators should use medical judgment in determining whether a particular symptom or sign is considered to be a part of COVID-19 infection clinical course or not and report them or not as AEs according to such determination. When a clear determination cannot be made by the investigators, a sign or symptom should be reported as AEs. All deaths irrespective of cause of death including due to COVID-19 during the study should be reported to the Sponsor using an SAE form.

Adverse events (including laboratory abnormalities that constitute AEs) should be described using a diagnosis whenever possible, rather than individual underlying signs and symptoms. When a clear diagnosis cannot be identified, each sign or symptom should be recorded as a separate AE.

The Investigator should ask the patient non-leading questions to determine if any AEs have occurred during the study, since the last study visit. Adverse events may also be recorded when they are volunteered by the patient, or through physical examination, laboratory tests, or other clinical assessments.

An AE should be followed until its resolution or until it is judged to be permanent, and assessment should be made at each visit (or more frequently, if necessary) of any changes in severity of the event, the suspected relationship to the study treatment, the interventions required to treat the event, and the outcome.

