### **8.2.1.3. Reporting of Serious Adverse Events**

Every SAE, regardless of the causal relationship to the study treatment, occurring after the patient has signed informed consent, until at least 30 days after the patient has stopped study treatment, must be reported to the Karyopharm Pharmacovigilance Department with the timeframe not to exceed 24 hours of the Investigator becoming aware of the event. The investigational site personnel must use the SAE Report Form provided by Karyopharm for reporting any SAE to the Karyopharm Pharmacovigilance Department.

Upon completion, the SAE Report Form must be immediately emailed or faxed to:

Pharmacovigilance Department  
Karyopharm Therapeutics Inc.  
Email: [[contact]](mailto:[contact])  
[contact] (USA)  
[contact] (Germany)

Any SAE observed after the 30-day follow-up period should only be reported to Karyopharm if the Investigator suspects that the SAE has a causal relationship to the study treatment. Recurrent episodes, complications, or progression of the initial SAE must be reported, as follow-up to the original episode, within 24 hours of the Investigator receiving the follow-up information.

An SAE should be followed until its resolution or until it is judged to be permanent. An assessment should be made at each study visit (or more frequently, if necessary) of any changes in severity of the event, the suspected relationship to the study treatment, the interventions required to treat the event, and the outcome of the event.

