## **9.5. Criteria for Stopping the Study**

The criteria to halt the study will depend on the number of patients enrolled at the time of the analysis as described below:

- A. If the overall number of patients enrolled is  $\leq 60$  patients, the study will be halted if any 1 of the following conditions are met at an IA or Data Safety Monitoring Board (DSMB) meeting:
  - 1. The absolute difference in the death rate in the treatment arm versus the control arm is  $>30\%$
  - 2. The absolute difference in the need for invasive ventilation in the treatment arm versus the control arm is  $>30\%$
  - 3. The absolute difference in the rate of Grade 3 or 4 nausea or vomiting in the treatment arm versus the control arm is  $>20\%$
- B. If the overall number of patients enrolled is  $>60$  patients, the study will be halted if any 1 of the following conditions are met at an IA or DSMB meeting:
  - 1. The absolute difference in the death rate in the treatment arm versus the control arm is  $>20\%$
  - 2. The absolute difference in the need for invasive ventilation in the treatment arm versus the control arm is  $>20\%$
  - 3. The absolute difference in the rate of Grade 3 or 4 nausea or vomiting in the treatment arm versus the control arm is  $>20\%$
- C. If the overall number of patients enrolled is  $>120$  patients, the study will be halted if any 1 of the following conditions are met at an IA or DSMB meeting:
  - 1. The absolute difference in the death rate in the treatment arm versus the control arm is  $>10\%$
  - 2. The absolute difference in the need for invasive ventilation in the treatment arm versus the control arm is  $>10\%$

3. The absolute difference in the rate of Grade 3 or 4 nausea or vomiting in the treatment arm versus the control arm is  $>10\%$

In addition, each IA includes a futility analysis which will determine if there is no significant improvement in the ordinal score in the treatment arm compared with the control arm.

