#### **10.5. Data Safety Monitoring Committee**

At the interim analyses, primary efficacy outcome and/or safety outcomes will be reviewed by the DSMB to determine if the trial will be stopped for futility or efficacy or continue as planned (Section 9.5). The DSMB will meet at least three times during the course of the study.

Enrollment will be paused for evaluation of safety and efficacy after the enrollment of the first 40 patients and the first meeting of the DSMB will occur within the first week of enrolling the 40th patient. No further patients will be enrolled until the completion of this DSMB review and the safety and efficacy data from the first 40 patients will be shared with the FDA prior to resuming enrollment. The remaining DSMB meetings are planned to evaluate the data from the IA. The DSMB may also meet at other times during the study as needed.

The independent DSMB will be composed of at least 3 members who are independent of Karyopharm and the study. The DSMB will meet to evaluate safety and efficacy, to ensure the appropriate benefit risk profile for patients enrolled in the study and to review any SAEs that occur during the study. The DSMB will be provided with all reports of AEs including SAEs regardless of Investigator causality assessments.

Details on how the DSMB will review safety and response data are provided in the DSMB Charter. The DSMB review will include, but not be limited to, evaluations of duration of therapy and all cause and AE-related dose reductions, interruptions, and discontinuations. At the interim analyses, primary efficacy outcome and selected safety outcomes will be reviewed by the DSMB to determine if the trial will be stopped for futility or efficacy or continue as planned.

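### Section 8.1.2 allows events judged to be COVID-19 course to go unrecorded as AEs, so non-serious Grade 3 vomiting can be missing from the nausea/vomiting halt rule and the Grade 3+ tables

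*Protocol*

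**What the plan says.** Protocol 8.1.2 opens with a general rule: "All AEs that begin or worsen after the patient has provided informed consent will be recorded". It then asks investigators to judge whether a clinical finding "is considered to be a part of COVID-19 infection clinical course or not and report them or not as AEs according to such determination". Two limits follow. One is a tie-break: "When a clear determination cannot be made by the investigators, a sign or symptom should be reported as AEs". The other protects deaths: "All deaths irrespective of cause of death including due to COVID-19 during the study should be reported to the Sponsor using an SAE form".

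Three other sections carry no such filter.

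- Protocol 8.1.1 defines an AE as any unfavourable sign, "symptom, or disease temporally associated with the use of study treatment, whether or not considered related to the study treatment". It counts worsening of an existing event as treatment-emergent, and its SAE definition has no COVID-19 exception.
- Protocol 8.2.1.2 requires SAEs to be entered in the eCRF, and 8.2.1.3 requires reporting of "Every SAE, regardless of the causal relationship to the study treatment, occurring after the patient has signed informed consent".
- Protocol 8.2.1.1 exempts only social, administrative and elective stays. The one explicit COVID-19 exemption for SAEs is for screen failures (4.3).

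The recorded events are used in two places. In Protocol 9.5, one halt condition is that "The absolute difference in the rate of Grade 3 or 4 nausea or vomiting in the treatment arm versus the control arm is" above 20% (rules A and B) or above 10% once more than 120 patients are enrolled (rule C). SAP 8.1 builds all its AE summaries, including the Grade 3 or higher tables, on recorded TEAEs.

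**The concern.** Protocol 8.1.2 applies a cause filter before an event reaches the database, whereas 8.1.1 defines events without regard to cause. No section says which prevails, so counts can depend on which one a site follows.

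In a blinded placebo-controlled trial, comparing the arms already separates drug effect from disease effect. Filtering by presumed cause at entry mainly shrinks the contrast that the safety tables and the nausea/vomiting rule should show.

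The overlap between disease and drug is documented. Protocol 1.2 lists fatigue, vomiting, diarrhea, headache, cough and dyspnea as COVID-19 symptoms. Table 7 reports the same six at low selinexor doses: 60%, 44%, 24%, 36%, 16% and 12% of 25 patients.

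An event left out at entry is hard to recover. Under 10.5, "The DSMB will be provided with all reports of AEs including SAEs regardless of Investigator causality assessments", but that covers only events that were reported.

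**Working it through.** **1. Which events have a second rule requiring them?**

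| Event attributed to COVID-19 | Under 8.1.2 | Required or captured elsewhere? |
|---|---|---|
| Death | Must be reported | Yes: 8.2.1.1 repeats it |
| Invasive ventilation | May be omitted as an AE | Yes: respiratory assistance in the eCRF (7.3.1), daily in-hospital ordinal score (7.3.2), own halt condition (9.5) |
| Other non-fatal serious event | May be omitted, if 8.1.2 is read as overriding | Yes, if 8.2.1.2 and 8.2.1.3 govern; precedence is not stated |
| Non-serious Grade 3 vomiting | May be omitted | No rule requires it as an AE: 8.1.2.1 says Grade 3 or 4 is not automatically serious |

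The last row is the clearest gap. Section 9.5 names no data source for its nausea/vomiting condition, and AE reporting is the only one the protocol describes that carries grades.

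**2. Effect on the threshold.** The documents give no rate of under-recording, so there is no stated figure to reproduce. Let p1 and p0 be the true Grade 3/4 nausea or vomiting rates on selinexor and placebo, and s the share recorded, assumed equal in both arms.

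Expected recorded difference = s × (p1 − p0). The true difference needed to reach a threshold T is therefore T/s.

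- T = 10 points: 10/0.9 = 11.1; 10/0.8 = 12.5; 10/0.7 = 14.3; 10/0.5 = 20.0.
- T = 20 points: 20/0.9 = 22.2; 20/0.8 = 25.0; 20/0.7 = 28.6; 20/0.5 = 40.0.

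**3. Effect on the chance of crossing.** Take the second interim analysis, about 124 patients (9.6), at an assumed even split of 62 per arm under rule C. With a events on selinexor and b on placebo, crossing needs (a − b)/62 > 0.10. Since 6/62 = 9.7% and 7/62 = 11.3%, this means a − b ≥ 7.

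P(cross) = sum over all a, b with a − b ≥ 7 of Bin(a; 62, s·p1) × Bin(b; 62, s·p0).

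| Assumed true rates | s = 1 | s = 0.8 | s = 0.5 |
|---|---|---|---|
| 18% vs 3% | 0.801 | 0.614 | 0.218 |
| 12% vs 2% | 0.445 | 0.261 | 0.053 |
| 8% vs 3% | 0.090 | 0.042 | 0.006 |

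**4. Are these rates plausible?** Table 7 shows no Grade 3 or 4 nausea or vomiting with onset by Day 14 in 25 patients. The exact two-sided 95% upper limit for 0 of 25 is 1 − 0.025^(1/25) = 13.7%. The 18% row lies above that limit and is the extreme case; the 12% and 8% rows lie within it.

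**The case against.** Two stronger readings are tempting. A reader might infer that non-fatal COVID-19 worsening enters the serious and Grade 3+ tables only if the patient dies. The documents do not support that. The carve-out speaks of a symptom or sign, unclear cases must be reported, and 8.2.1.2 and 8.2.1.3 still require every SAE. Nothing says that 8.1.2 overrides them. A reader might also infer that an excess of intubation on selinexor could go unseen. It could be missing from a serious-TEAE table, but not from the eCRF respiratory-assistance data, the ordinal score, the invasive-ventilation halt condition or the rate of mechanical ventilation, a key secondary endpoint.

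On the nausea/vomiting rule, several counterpoints stand in part.

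- Protocol 1.2 lists vomiting (5%) but not nausea, so attribution of nausea to COVID-19 is less likely. No document figure supports any particular value of s.
- Grade 3 nausea or vomiting leads to interruption under Table 5, and 5.7 requires modifications to be documented with a reason. But 5.7 and the Table 5 footnote tie dose changes to selinexor reactions, so an event attributed to COVID-19 may leave no such trace. Section 6.2 does record the reason for stopping treatment, which covers only cases that end in discontinuation.
- The six overlapping symptoms were Grade 1 or 2 only in Table 7, so the overlap shows that misattribution is possible, not how often it would reach Grade 3.
- The DSMB Charter, which is not among the documents, may specify other inputs.

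Separating disease course from AEs in hospitalised severe COVID-19 is also a reasonable aim. That argues for flagging such events rather than leaving Grade 3 or higher events unrecorded.

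**Conclusion.** The conflict between 8.1.2 and 8.1.1 is real, as is the one within 8.1.2. Only deaths are expressly protected from the carve-out. Capture of other non-fatal COVID-19 worsening depends on site judgement and on which section prevails.

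The consequence that matters most is narrow: non-serious Grade 3 vomiting attributed to COVID-19 can go unrecorded, so the 9.5 nausea/vomiting rule and the SAP Grade 3+ tables can run on incomplete counts. The death and invasive-ventilation halt rules do not depend on AE classification and are unaffected.

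The size cannot be derived from the documents. Loss of a fifth of events in both arms would raise the true difference needed from 10 to 12.5 points and lower the chance of crossing by about 5 to 19 percentage points across the three assumed scenarios (0.090 to 0.042; 0.801 to 0.614). These figures rest on assumed event rates, an even split and equal under-recording. Blinding (6.4) makes equal under-recording plausible, but it could fail if nausea reveals the assignment. This is a cheap improvement worth making, not a threat to the efficacy conclusions.

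**What to change.** In Protocol 8.1.2, state that the COVID-19 carve-out does not limit 8.2.1.2 and 8.2.1.3, and that it does not apply to Grade 3 or higher events or to nausea or vomiting of any grade. After first dose, record all of these as AEs whatever the presumed cause, with an eCRF flag marking those consistent with COVID-19 course. In 9.5, name the AE data as the source for the nausea/vomiting check and use all records, flagged or not. In SAP 8.1, build the tables on all records and show the flagged subset separately.

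This changes recording only, not patient management. The carve-out stays for non-serious Grade 1 and 2 events other than nausea and vomiting, so most of the low-grade symptom overlap remains filtered; that is a deliberate limit on site burden. The cost is a protocol wording change, one eCRF field, more AE entries, and higher reported AE rates in both arms.

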#### **8.1.2.1. Laboratory Test Abnormalities**

Laboratory abnormalities that constitute an AE in their own right (i.e., are considered to be clinically significant, induce clinical signs or symptoms, require concomitant therapy, or require changes in study treatment), should be recorded on the Adverse Events eCRF. Whenever

possible, a diagnosis, rather than a symptom should be provided (e.g., anemia instead of low hemoglobin).

Laboratory abnormalities that meet the criteria for an AE should be followed until they have returned to baseline levels (as measured during the Screening visit) or an adequate explanation of the abnormality is identified. When an abnormal laboratory or test result corresponds to a sign/symptom of an already reported AE, it is not necessary to separately record the laboratory/test result as an additional event.

A laboratory abnormality that does not meet the definition of an AE should not be reported as an AE. A Grade 3 or 4 event (considered to be severe per NCI CTCAE, v. 5.0) does not automatically indicate an SAE unless it meets the definition of serious as defined in Section 8.1 and/or as per the opinion of the Investigator. A laboratory abnormality that results in a dose being held or modified would, by definition, be an AE and must be recorded as such in the eCRF.

